## 7.1.4.7 Tumor tissue collection and correlative studies blood sampling

See section 4.2.

## 7.1.5 Laboratory Procedures/Assessments

Details regarding specific laboratory procedures/assessments to be performed in this trial are provided below Laboratory Safety Evaluations (Hematology, Chemistry and Urinalysis)

Laboratory tests for hematology, chemistry, urinalysis, and others are specified in **Table 9**.

**Table 9. Laboratory Tests** 

Hematology	Chemistry	Urinalysis	Other
Hematocrit	Albumin	Blood	Serum β-human chorionic gonadotropin†
Hemoglobin	Alkaline phosphatase	Glucose	(β-hCG)†
7.1.5.1.1 Pplatelet count	Alanine aminotransferase (ALT)	Protein	PT (INR)
WBC (total and differential)	Aspartate aminotransferase (AST)	Specific gravity	aPTT
Red Blood Cell Count		Microscopic exam (If abnormal)	Total thriiodothyronine (T3)
Absolute Neutrophil Count	Carbon Dioxide ‡	results are noted	Free tyroxine (T4)
Absolute Lymphocyte Count	(CO 2 or biocarbonate)	Urine pregnancy test †	Thyroid stimulating hormone (TSH)
	Calcium		
	Chloride		Blood for correlative studies
	Glucose		
	Potassium		
	Sodium		
	Magnesium		
	Total Bilirubin		
	Direct Bilirubin (If total bilirubin is elevated above the upper limit of normal)		
	Total protein		
	Blood Urea Nitrogen		

† Perform on women of childbearing potential only. If urine pregnancy results cannot be confirmed as negative, a serum pregnancy test will be required. ‡ If considered standard of care in your region.

Laboratory tests for screening or entry into the Second Course Phase should be performed within 10 days prior to the first dose of treatment. Any screening labs done within 7 days of C1D1 do not need to be repeated prior to first treatment. After Cycle 1, pre-dose laboratory procedures can be conducted up to 72 hours prior to dosing. Results must be reviewed by the investigator or qualified designee and found to be acceptable prior to each dose of trial treatment.

## 7.1.5.2 Pharmacodynamic evaluations

See section 4.3.3.1.

#### **Blood Collection for Anti-Pembrolizumab Antibodies**

#### 7.1.6 Other Procedures

#### 7.1.6.1 Withdrawal/discontinuation

When a subject discontinues/withdraws prior to trial completion, all applicable activities scheduled for the final trial visit should be performed at the time of discontinuation. Any adverse events which are present at the time of discontinuation/withdrawal should be followed in accordance with the safety requirements outlined in Section 7.2 - Assessing and Recording Adverse Events. Subjects who a) attain a CR or b) complete 24 months of treatment with pembrolizumab may discontinue treatment with the option of restarting treatment if they meet the criteria specified in Section 7.1.7.3. After discontinuing treatment following assessment of CR, these subjects should return to the site for a Safety Follow-up Visit (described in Section 7.1.5.3.1) and then proceed to the Follow-Up Period of the study (described in Section 7.1.5.4).

### 7.1.7 Visit Requirements

Visit requirements are outlined in Section 6.0 - Trial Flow Chart. Specific procedure-related details are provided above in Section 7.1 - Trial Procedures.

### 7.1.7.1 Safety follow-up visit

The mandatory Safety Follow-Up Visit should be conducted approximately 30 days after the last dose of trial drug administration or before the initiation of a new anti-cancer treatment, whichever comes first. All AEs that occur prior to the Safety Follow-Up Visit should be recorded. Subjects with an AE of Grade > 1 will be followed until the resolution of the AE to Grade 0-1 or until the beginning of a new anti-neoplastic therapy, whichever occurs first. SAEs that occur within 90 days of the end of treatment or before initiation of a new anti-cancer treatment should also be followed and recorded. Subjects who are eligible for retreatment with pembrolizumab (as described in Section 7.1.7.3) may have up to two safety follow-up visits, one after the Treatment Period and one after the Second Course Phase.

#### 7.1.7.2 Follow-up visits

Subjects who discontinue trial treatment for a reason other than disease progression will move into the Follow-Up Phase and should be assessed every 8 weeks (56  $\pm$  7 days) by radiologic imaging to monitor disease status. After 1 year, the imaging time point will occur

every 12 weeks (± 7 days). Every effort should be made to collect information regarding disease status until the start of new anti-neoplastic therapy, disease progression, death, end of the study or if the subject begins retreatment with pembrolizumab as detailed in Section 7.1.7.3. Information regarding post-study anti-neoplastic treatment will be collected if new treatment is initiated.

Subjects who are eligible to receive retreatment with pembrolizumab according to the criteria in Section 7.1.7.3 will move from the follow-up phase to the Second Course Phase when they experience disease progression.

## 7.1.7.2.1 Survival Follow-up

Once a subject experiences confirmed disease progression or starts a new anti-cancer therapy, the subject moves into the survival follow-up phase and should be contacted by telephone every 12 weeks to assess for survival status until death, withdrawal of consent, or the end of the study, whichever occurs first.

## 7.1.7.3 Second course phase (retreatment period)

Subjects who stop pembrolizumab with SD or better may be eligible for up to one year of additional pembrolizumab therapy if they progress after stopping study treatment. This retreatment is termed the Second Course Phase of this study and is only available if the study remains open and the subject meets the following conditions:

#### Either

- Stopped initial treatment with pembrolizumab after attaining an investigatordetermined confirmed CR according to RECIST 1.1, and
  - Was treated for at least 24 weeks with pembrolizumab before discontinuing therapy
  - Received at least two treatments with pembrolizumab beyond the date when the initial CR was declared

#### OR

 Had SD, PR or CR and stopped pembrolizumab treatment after 24 months of study therapy for reasons other than disease progression or intolerability

#### **AND**

- Experienced an investigator-determined confirmed radiographic disease progression after stopping their initial treatment with pembrolizumab
- Did not receive any anti-cancer treatment since the last dose of pembrolizumab
- Has a performance status of 0 or 1 on the ECOG Performance Scale
- Demonstrates adequate organ function as detailed in Section 5.1.2

- Female subject of childbearing potential should have a negative serum or urine pregnancy test within 72 hours prior to receiving retreatment with study medication.
- Female subject of childbearing potential should be willing to use 2 methods of birth control or be surgically sterile, or abstain from heterosexual activity for the course of the study through 120 days after the last dose of study medication (Reference Section 5.7.2). Subjects of child bearing potential are those who have not been surgically sterilized or have been free from menses for > 1 year.
- Male subject should agree to use an adequate method of contraception starting with the first dose of study therapy through 120 days after the last dose of study therapy.
- Does not have a history or current evidence of any condition, therapy, or laboratory abnormality that might interfere with the subject's participation for the full duration of the trial or is not in the best interest of the subject to participate, in the opinion of the treating investigator.

Subjects who restart treatment will be retreated at the same dose and dose interval as when they last received pembrolizumab. Treatment will be administered for up to one additional year.

Visit requirements are outlined in Section 6.0 – Trial Flow Chart.

## 7.2 Assessing and Recording Adverse Events

An adverse event is defined as any untoward medical occurrence in a patient or clinical investigation subject administered a pharmaceutical product and which does not necessarily have to have a causal relationship with this treatment. An adverse event can therefore be any unfavorable and unintended sign (including an abnormal laboratory finding, for example), symptom, or disease temporally associated with the use of a medicinal product or protocol-specified procedure, whether or not considered related to the medicinal product or protocol-specified procedure. Any worsening (i.e., any clinically significant adverse change in frequency and/or intensity) of a preexisting condition that is temporally associated with the use of the Merck's product, is also an adverse event. The start of AE collections will be C1D1. Abnormal Lab values, vital signs or test results that do not induce clinical signs/symptoms or require therapy, will not be considered clinically significant and will not be reported as Adverse Events.

Changes resulting from normal growth and development that do not vary significantly in frequency or severity from expected levels are not to be considered adverse events. Examples of this may include, but are not limited to onset of menses or menopause occurring at a physiologically appropriate time.

Merck product includes any pharmaceutical product, biological product, device, diagnostic agent or protocol-specified procedure, whether investigational (including placebo or active comparator medication) or marketed, manufactured by, licensed by, provided by or distributed by Merck for human use.

Adverse events may occur during the course of the use of Merck product in clinical trials or within the follow-up period specified by the protocol, or prescribed in clinical practice, from overdose (whether accidental or intentional), from abuse and from withdrawal.

Adverse events may also occur in screened subjects during any pre-allocation baseline period as a result of a protocol-specified intervention, including washout or discontinuation of usual therapy, diet, placebo treatment or a procedure.

Progression of the cancer under study is not considered an adverse event unless it is considered to be drug related by the investigator.

All adverse events will be recorded from C1D1 through 30 days following cessation of treatment and at each examination on the Adverse Event case report forms/worksheets. The reporting timeframe for adverse events meeting any serious criteria is described in section 7.2.3.1.

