### Vorinostat in Lung Cancer.

Suberoylanilide hydroxamic acid (SAHA, vorinostat) is an orally active, small molecule inhibitor of histone deacetylase (HDACi). Clinical trials have shown that daily oral vorinostat is safe and tolerable and has a broad range of clinical activity in advanced solid tumors.

Vansteenkiste et al. conducted a phase II trial of oral vorinostat in 16 patients with breast cancer (3 patients), NSCLC (10 patients), and colorectal cancer (3 patients). Patients were treated with oral vorinostat 200mg BID, 300mg BID, or 400mg BID for 14 days on, 7 days off on a 21-day cycle. Dose-limiting toxicities occurred in a total of 6 patients at both the 300mg BID and 400mg BID doses and included weight loss, asthenia, thrombocytopenia, nausea, vomiting, and anorexia. Grade 3/4 toxicities included thrombocytopenia (50%), anemia (12%), asthenia (12%), nausea (12%), and anorexia (6%). No dose limiting toxicities

[figure not shown]
occurred at the 200mg BID dose level. Although treatment duration was short and TTP was 33.5 days, 6/10 patients with NSCLC had a best response of stable disease by RECIST (Vansteenkiste et al., 2008). Kelly et al. conducted a phase I study that enrolled 50 patients with solid tumors and 23 patients with hematologic malignancies. The maximum tolerated dose was vorinostat 400mg daily or 200mg bid for continuous daily dosing and 300mg bid for 3 of 7 consecutive days. In addition to the dose-limiting toxicities outlined in the prior trial, one patient had elevation of liver enzymes. Only two patients with lung cancer were enrolled in that study; there were two patients with partial responses (laryngeal cancer and mesothelioma) (Kelly et al., 2005). Ma et al. studied vorinostat in a preclinical model with a window of opportunity trial in 15 patients with early-stage lung and esophageal cancers (Ma et al., 2013). Vorinostat 400mg daily was given for 2-9 days and patients had pre-therapy and post-therapy biopsies of target lesions. The study included 10 evaluable patients (8 with lung adenocarcinoma, one with lung squamous cell cancer, and one with esophageal adenocarcinoma). Eight of 9 lung cancer post-treatment biopsies exhibited either acute or chronic inflammation or necrosis when compared to pre-treatment biopsies. Additionally, there was evidence of CD8 positive tumor infiltrating lymphocytes in the post-treatment tissue, supporting the theory that vorinostat acts as a biologic effector of tumor immunogenicity.

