#### The following will be DLTs:

- Any Grade 4 immune-related adverse event (irAE)
- Any ≥ Grade 3 colitis
- Any Grade 3 or 4 non-infectious pneumonitis irrespective of duration
- Any Grade 2 pneumonitis that does not resolve to ≤ Grade 1 within 3 days of the initiation of maximal supportive care
- Any Grade 3 irAE, excluding colitis or pneumonitis, that does not downgrade to Grade 2 within 3 days after onset of the event despite optimal medical management including systemic corticosteroids or does not downgrade to ≤ Grade 1 or baseline within 14 days
- Liver transaminase elevation > 8 × upper limit of normal (ULN) or total bilirubin > 5 × ULN
- Any ≥ Grade 3 non-irAE, except for the exclusions listed below

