#### The definition excludes the following conditions:

- Grade 3 fatigue lasting ≤ 7 days
- Grade 3 endocrine disorder (thyroid, pituitary, and/or adrenal insufficiency) that is managed with or without systemic corticosteroid therapy and/or hormone replacement therapy and the subject is asymptomatic
- Grade 3 inflammatory reaction attributed to a local antitumor response (eg, inflammatory reaction at sites of metastatic disease/lymph nodes)
- Concurrent vitiligo or alopecia of any AE grade
- Grade 3 infusion-related reaction (first occurrence and in the absence of steroid prophylaxis) that resolves within 6 hours with appropriate clinical management
- Grade 3 or 4 neutropenia that is not associated with fever or systemic infection that improves by at least 1 grade within 3 days. Grade 3 or Grade 4 febrile neutropenia will be a DLT regardless of duration or reversibility
- Grade 3 or 4 lymphopenia
- Grade 3 thrombocytopenia that is not associated with clinically significant bleeding that requires medical intervention, and improves by at least 1 grade within 3 days

- Isolated Grade 3 electrolyte abnormalities that are not associated with clinical signs or symptoms and are reversed with appropriate maximal medical intervention within 3 days
- Grade 3 amylase or lipase abnormality that is not associated with symptoms or clinical manifestations of pancreatitis
- Immune-related AEs are defined as AEs of an immune nature (ie, inflammatory) in the
  absence of a clear alternative etiology. In the absence of a clinically significant
  abnormality, repeat laboratory testing will be conducted to confirm significant
  laboratory findings prior to designation as a DLT. Laboratory abnormalities that are
  not deemed to be clinical significant will not be considered a DLT.

While the rules for adjudicating DLTs in the context of dose exploration are specified above, an AE not listed above may be defined as a DLT after a consultation with the sponsor and investigators, based on the emerging safety profile.

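### If the adverse-event rule's meaning of clinical significance is carried into the DLT section, silent Grade 3-4 laboratory toxicities, mainly untreated cytopenias, can go unrecorded and uncounted

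*Combined protocol and SAP*

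**What the plan says.** Section 7.2 defines an adverse event broadly, "including an abnormal laboratory finding, for example". The same paragraph then narrows it: laboratory values, vital signs and test results that produce no signs or symptoms and need no therapy "will not be considered clinically significant and will not be reported as Adverse Events". No CTCAE grade is exempt.

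Section 8.2.2 defines a DLT as any Grade 3 or higher toxicity in the evaluation period. Its list counts "Liver transaminase elevation > 8 × upper limit of normal (ULN) or total bilirubin > 5 × ULN" on the value alone, and "Any ≥ Grade 3 non-irAE, except for the exclusions listed below". The exclusions are narrow. One covers "Grade 3 thrombocytopenia that is not associated with clinically significant bleeding that requires medical intervention", and only if it improves by at least one grade within 3 days. Others cover Grade 3-4 lymphopenia, isolated reversible Grade 3 electrolyte changes, and Grade 3 amylase or lipase changes without symptoms. The exclusions close with a general sentence: laboratory abnormalities "not deemed to be clinical significant will not be considered a DLT". Section 8.2.2 does not say what makes a laboratory finding clinically significant.

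**The concern.** The only working definition of clinical significance for a laboratory value is the one in 7.2. An investigator who carries it into the last sentence of the 8.2.2 exclusions removes from the DLT count every laboratory event that is silent and untreated, at any grade. The list itself would count several of these: Grade 4 platelets without bleeding or transfusion, Grade 3 platelets that do not improve within 3 days, and Grade 3 anemia without transfusion.

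Safety is the Phase I primary objective. Twelve patients set the vorinostat dose for Phase Ib and for Arm B of Phase II, and Section 4.2.1 names cytopenias as the toxicity that occurs with vorinostat. In cohorts of three, one event more or less can change the next dose.

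**Working it through.** **Setting the texts side by side.** Take a Grade 4 platelet count with no bleeding and no treatment.

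- Section 7.2: no signs or symptoms and no therapy, so not clinically significant and not an adverse event.
- 8.2.2 list: a Grade 3 or higher event that no specific exclusion covers, so a DLT.
- 8.2.2 closing laboratory sentence: not a DLT if 7.2's meaning applies; undetermined if it does not.

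The specific exclusion for amylase or lipase changes without symptoms would be unnecessary, and those for platelets and electrolytes largely so, if every silent untreated value were already out. That suggests the list was not written with the 7.2 rule in mind.

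**Inputs for the size** (8.2.1 and 8.2.3). Target DLT rate 30%; initial guesses 1%, 10% and 30% at 100, 200 and 400 mg; cohorts of 3, 12 patients, starting at 200 mg. The model is P(DLT at dose k) = exp(3 + θd_k) / (1 + exp(3 + θd_k)), with θ ~ Gamma(1, 1). The plan does not give the standardized doses. I assume d_k = logit(initial guess) − 3, so that θ = 1 returns the guesses: d = −7.595, −5.197 and −3.847. Two estimates are shown: plug-in (the model at the posterior mean of θ) and average (the DLT probability averaged over the posterior).

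**Reproducing Table 11** (estimate at 400 mg):

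| Data | Plan | Plug-in | Average |
|---|---|---|---|
| 0/3 at 200 | 10.9% | 2.0% | 14.8% |
| then 1/3 at 400 | 25.5% | 22.1% | 26.9% |
| then 2/6 at 400 | 28.7% | 27.0% | 29.6% |
| then 3/9 at 400 | 30.1% | 29.0% | 30.8% |

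Neither version matches exactly, but the plan's figure lies between the two at every step, so results are given as ranges.

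**One uncounted DLT in the first 400 mg cohort**, after 0/3 at 200 mg:

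- 2/3 counted, plug-in: 18.6% at 200 mg and 42.3% at 400 mg. Distances from 30% are 11.4 and 12.3 points, so 200 mg is recommended, narrowly.
- 2/3 counted, average: 23.5% and 43.5%. Distances are 6.5 and 13.5 points, so 200 mg is recommended.
- 1/3 counted: 22.1% (plug-in) or 26.9% (average) at 400 mg, against 6.0% or 11.2% at 200 mg, so 400 mg is kept.

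**One uncounted DLT in the worked example.** With 2/9 instead of 3/9 at 400 mg, the estimate falls from 29.0% to 19.2% (plug-in) or from 30.8% to 21.9% (average). The recommendation stays at 400 mg; only the estimated risk changes.

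**Operating characteristics.** Exact enumeration with the plug-in version gives a 25.4% chance of selecting 400 mg in Scenario 3 (true rates 10/30/50%, so 400 mg is above the true MTD); Table 13 states 25.1%. The 400 mg figures for the other scenarios also agree within 0.2 points (83.3, 8.8 and 83.3 against 83.3, 8.9 and 83.5). The split between 100 and 200 mg in Scenarios 2 and 3 did not reproduce. The documents do not give the share of DLTs that would be lost, so 10%, 25% and 50%, equal at every dose, are pure assumptions. They raise the Scenario 3 chance to 34.7%, 50.9% and 78.2%. Across both estimates, with and without the 8.2.3 step down to 100 mg after a DLT in the first cohort, the ranges are 19.4-25.4% with no loss, then 27.2-34.7%, 41.6-50.9% and 68.9-78.2%.

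**The case against.** The strongest reply is that 8.2.2 stands on its own. It contains no symptom-or-therapy test and does not refer to 7.2. It speaks of toxicity rather than reported adverse events, and its preceding sentence provides for repeat testing to confirm a finding before it is designated a DLT, which leaves room to count a silent value. A reader who lets the specific list override the general adverse-event rule loses nothing. This stands as far as it goes: it would be wrong to infer that 8.2.2 repeats the 7.2 rule. But the term remains undefined where it decides the count, and the closing discretion clause of 8.2.2 extends only to an AE not listed, which under 7.2 a silent value is not.

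A reader might also infer that a transaminase above the listed threshold escapes both records. For many hepatic events it would not. Section 5.6.1 treats Grade 2 and higher hepatic events with corticosteroids, so they require therapy and are adverse events under 7.2 itself, and 7.2.3.2 makes a combined transaminase and bilirubin elevation (with alkaline phosphatase below 2 × ULN) reportable on laboratory values alone. The limits are that 5.6.1 applies to events judged related to pembrolizumab, and that the reportable combination does not cover an isolated rise. Neither provision reaches cytopenias.

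The 50% Grade 3/4 thrombocytopenia in Section 4.2.1 cannot be used as a rate for this trial. It comes from 16 patients on 200 to 400 mg twice daily for 14 of 21 days, whereas the maximum here is 400 mg once daily. That study had no DLTs at 200 mg twice daily, the same total daily dose, and the protocol does not say how many of its cases were silent and untreated.

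Finally, a distorted adverse-event comparison between Arms A and B might be inferred. Section 8 plans no such comparison, and the winner is chosen on response alone. Only Arm B receives vorinostat, so any under-recording of its laboratory toxicity would fall mainly there. Blood counts and chemistry are scheduled every cycle and laboratory data are stored (7.1.2), so a graded table could be produced, but none is planned.

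**Conclusion.** The conflict is in the current text and should be resolved. Followed literally, with the 7.2 meaning carried into 8.2.2, the rules can drop events that the DLT list counts. The exposure is mainly silent, untreated Grade 3-4 cytopenias.

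The direction is certain: the rule can only remove DLTs, which makes the combination appear safer and favors the higher dose. The size is not known. It depends on how investigators read 8.2.2 and on how many DLTs are laboratory-only, silent and untreated; the documents settle neither. So the combination can look safer than it is; that it will is not supported. One lost event is enough to move the recommendation after the second cohort from 200 mg to 400 mg under both calculations, although narrowly under plug-in, and to lower the final estimate in the worked example from about 29-31% to 19-22%. These figures rest on the assumed standardized doses.

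**What to change.** Make three wording changes.

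1. In 7.2, record CTCAE Grade 3 or higher laboratory abnormalities from protocol-scheduled tests as adverse events, whether or not they cause symptoms or need therapy.
2. In 8.2.2, state what clinically significant means for DLT purposes and who decides it.
3. Reconcile the 7.2 rule, the DLT list and the closing laboratory sentence of the exclusions, so that all three count the same events.

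Which laboratory values are DLTs is a clinical decision for the sponsor and investigators. A laboratory toxicity table by CTCAE grade and arm would be a useful addition to Section 8, but would not by itself repair the DLT count. The cost is wording plus modest extra data entry; the tests are already scheduled.
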